**Secondary:**

- Change in HbA1c from baseline to 12 weeks (+/-2 weeks) post-discharge
- Change in fasting plasma glucose (FPG) from baseline in DOS vs ESC
- % of patients achieving HbA1C 7% in DOS vs ESC
- % of patients achieving HbA1C 6.5% in DOS vs ESC
- % of patients achieving individualized HbA1c target in DOS vs. ESC: HEDIS HbA1c target (<8% if age  $\geq$  65 years or known history of ischemic vascular disease, heart failure, advanced kidney disease [eGFR <30], dementia, proliferative retinopathy/blindness, advanced neuropathy [history of ulcer or amputation] or history of severe hypoglycemia; otherwise goal is <7%)
- Proportion of patients with accurate and complete discharge orders for insulin and related supplies.
- Adherence to glargine U300 (>80% of doses) at 2, and 24 weeks
- Proportion of patients who remain on glargine U300 at 24 weeks
- Mean dose of glargine U300 at 2 and 24 weeks
- Proportion of patients who follow up with their primary care provider within 2, 6 weeks of discharge
- Incidence of documented symptomatic (BG <54 mg/dl) hypoglycemia

**Analysis:** Outcomes will be further analyzed by type of diabetes, pre-admission therapy, and bolus insulin requirements.

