### D.2. Research Design

**D.2.a Study Design:** In this 24 week randomized controlled trial, hospitalized insulin-requiring patients with type 2 diabetes and poor glycemic control (HbA1c >8.5%) will receive standard of care insulin therapy including basal insulin glargine U300 (TOUJEO®) plus additional background therapy (non-insulin and prandial insulin therapies) with either a diabetes focused discharge order set (DOS) and follow-up communication to facilitate insulin titration and outpatient follow-up or enhanced standard care (ESC).

**D.2.b Study Population:** 222 patients (type 2 diabetes) will be recruited. Inclusion/exclusion criteria appear in Table 6. Hospitalized patients with type 2 diabetes (HbA1c >8.5%) who are receiving basal insulin at least 10 unit per day and are able to provide informed consent will be approached.

Patients must have access to some form of communication (phone, electronic patient messaging) post discharge and be willing to obtain HbA1c at follow-up. Patients will be identified through daily screening of the inpatient medical and surgical services throughout the institution.

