#### H.1.a. Missing Data

All data analyses will be completed as intention to treat analyses (i.e., individuals analyzed by group according to original random assignment, without regard to adherence to the intervention).

Longitudinal outcomes (e.g., HbA1c) will be analyzed using mixed models utilizing all available measurements from individuals randomized. Missing binary outcomes (e.g., accurate and complete discharge orders, adherence) and missing covariate data will be imputed, using multiple imputation in SAS v9.3 PROC MI.

Table 9. Study Procedures and Visits

Visit number	0	1	2	3	4
Time of Visit	Screen/consent	2 week	6 week	12 week	24 week
Type of visit	In-person	Phone	Phone	In-person	In-person
Informed consent/contact team	x				
Randomization	x				
Load DOS into EMR and inform discharge team	x				
Provide study drug and glucose monitoring instructions	x				
Demographics/Socioeconomic status	x				
Diabetes history	x				
Hospitalization history	x				
PSS scale	x				
DES-SF	x			x	x
Newest Vital Sign	x				
Glucose/insulin diary	x				
Review DOS		x			
Ascertain health care utilization		x	x	x	x
Review glucose/insulin diary		x	x	x	x
Hypoglycemia/Hyperglycemia		x	x	x	x
Review insulin adherence, persistence		x	x	x	x
Nurse counsellor (DOS group only)		x	x	x	x
HbA1c	x			x	x
Fasting blood glucose	x			x	x

DOS=discharge order set, EMR=electronic medical record, PSS=Perceived Social Support scale, DES-SF=Diabetes empowerment scale-short form, In-Person clinic visits will be conducted at either CarPoint East or McCampbell Hall

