### H.2.a. Statistical Power and Sample Size

The sample size for our study was based on a comparison of change in HbA1c over three months adjusting for baseline covariates related to change in HbA1c: age, whether or not patient is new to insulin, and dose of insulin; the first two were selected based on our preliminary data and the latter was selected based on an expected relationship. The following expression, adapted from Oakes and Feldman, was used to calculate the number of individuals per group:

$$n/group = \frac{4\sigma^2(1-\rho)(1-R^2)(Z_{1-\alpha/2} + Z_{1-\beta})^2}{\Delta^2}$$

where  $\sigma$  is the standard deviation of HbA1c,  $\rho$  is the correlation between baseline and 24 week HbA1c levels,  $R^2$  is the proportion of variability in change in HbA1c explained by the baseline covariates,  $\Delta$  is the difference in change in HbA1c between treatment groups, and  $Z_{1-\alpha/2}$  and  $Z_{1-\beta}$  are standard normal quantiles calculated at the two-sided type-I error rate ( $\alpha$ ) and power (1- $\beta$ ). Using parameter values based on our preliminary data ( $\sigma = 2.2\%$ ,  $\rho = 0.25$ ,  $R^2 = 0.5$ ) and based on the effect observed by Wexler ( $\Delta = 0.8\%$ ), we will need 89 individuals per treatment group with 24 week follow-up to achieve 80% power at  $\alpha = 0.05$ . Since we expect 20% attrition, we will recruit 111 individuals per group into our study. The study is powered to detect a difference in the primary endpoint only. However, additional secondary endpoints of strong interest are pre-specified and included in the analysis.

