**Secondary:**

- Difference in the change in HbA1c from baseline to 12 weeks (+/-2 weeks) post-discharge (%, mmol/l)
- Difference in the change in HbA1c from baseline to 12 and 24 weeks (+/-2 weeks) post-discharge (%, mmol/l)
- Difference in the change in fasting plasma glucose (FPG) from baseline to 12 and 24 weeks in DOS vs ESC (mg/dl)
- Difference in the % of patients achieving HbA1C 7% in DOS vs ESC (12, 24 weeks)
- Difference in the % of patients achieving HbA1C 6.5% in DOS vs ESC (12, 24 weeks)
- Difference in the % of patients achieving individualized HbA1C target in DOS vs ESC (12, 24 weeks)
- Difference in the proportion of patients with accurate and complete discharge orders for basal insulin and related supplies. (%)
  - Assessed as complete dose, quantity dispensed, adequate refills (separate for basal and prandial insulin), and correct prescription for pen needles (presence, quantity, adequate refills), no jargon
- Difference in the proportion of patients with accurate and complete discharge orders for prandial insulin and related supplies. (%)
  - Assessed as complete dose, clear dosing instructions, quantity dispensed, adequate refills, and correct prescription for pen needles (presence, quantity, adequate refills), no jargon
- Difference in the proportion of patients with a discharge prescription for glucose monitoring supplies (%)
- Difference in adherence to glargine U300 (% taking >80% of doses) at 2, and 24 weeks
- Difference in the proportion of patients who remain on glargine U300 at 24 weeks (%)
- Difference in the mean dose of glargine U300 at 2 and 24 weeks (units)
- Difference in the frequency of glucose monitoring at 2 and 24 weeks (times per day)
- Difference in the proportion of patients who follow up with their primary care provider or endocrinologist within 2, 6 weeks of discharge (%)
- Difference in the incidence of documented symptomatic (BG <54 mg/dl) hypoglycemia (%)

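### The hypoglycaemia percentage has no stated observation window, and no planned rule uses the weeks for which early leavers were observed

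*Combined protocol and SAP*

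**What the plan says.** H.2.b lists, among the secondary endpoints, "Difference in the incidence of documented symptomatic (BG <54 mg/dl) hypoglycemia", with percent as the unit. The synopsis has the same item, "Incidence of documented symptomatic (BG <54 mg/dl) hypoglycemia", also without a window. Every other post-discharge endpoint in the H.2.b list carries a time, for example "Difference in adherence to glargine U300 (% taking >80% of doses) at 2, and 24 weeks".

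The trial is described in D.2.a with the words "In this 24 week randomized controlled trial". Table 9 has hypoglycaemia collected at the 2, 6, 12 and 24 week contacts.

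On losses, H.2.a states: "Since we expect 20% attrition, we will recruit 111 individuals per group into our study". On missing data, H.1.a states: "Missing binary outcomes (e.g., accurate and complete discharge orders, adherence) and missing covariate data will be imputed", by multiple imputation. H.2.d describes the imputation model for the binary secondary outcomes. It uses treatment arm and covariates measured at baseline, and results are pooled by Rubin's rules into a two-sample test of proportions. The aims listed in H.2.d do not include hypoglycaemia.

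No section says whether a patient last reached at week 2, 6 or 12 counts as a non-event, as missing, or as an event if one had already been reported. No rate or time-to-event analysis is planned.

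**The concern.** A patient who leaves after week 6 without an event is neither a 24-week non-event nor wholly missing: six weeks are known and eighteen are not. A plain percentage has no place for that information. Scored as a non-event, the unobserved time is treated as free of hypoglycaemia. Imputed from arm and baseline data alone, the patient receives the full 24-week risk and the six event-free weeks are ignored.

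This is the only safety comparison between arms in H.2.b. Severe hypoglycaemia appears in the safety monitoring plan as a reportable adverse event, but no between-arm analysis of it is described. The arms differ in titration instructions and in who makes the follow-up contacts (Table 7), so readers will look to this percentage for any difference in harm. If the scoring rule is chosen after the data are seen, the result can shift with the choice. If the arms differ in retention, part of any difference may reflect time under observation.

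**Working it through.** **The plan's own figures.** The only stated numbers are those for the primary endpoint. The H.2.a formula with σ = 2.2, ρ = 0.25, R² = 0.5, Δ = 0.8, 80% power and 5% two-sided error gives

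4 × 2.2² × 0.75 × 0.5 × 7.849 / 0.8² = 89.04 per group,

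which matches "we will need 89 individuals per treatment group with 24 week follow-up to achieve 80% power at" the stated error rate. Then 89 / 0.8 = 111.25, matching the 111 recruited. The attrition allowance is applied correctly and amounts to about 22 patients per group (111 − 89).

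**Assumptions.** The documents give no hypoglycaemia rate, no leaving times and no attrition by arm. I assume a constant hazard, a 24-week risk p of 10%, 20% or 30%, and last contact spread equally over weeks 2, 6 and 12. I also assume that all of the expected attrition is loss of hypoglycaemia data.

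**Risk observed in leavers.** With q(w) = 1 − (1 − p)^(w/24) and p = 0.20:

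- q(2) = 0.0184, q(6) = 0.0543, q(12) = 0.1056
- mean e = 0.0594

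**Reported incidence in one arm, attrition a = 0.20, true value 20%.**

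1. Leavers scored as observed: (1 − a)p + ae = 0.16 + 0.2 × 0.0594 = 0.172.
2. Observed events kept, event-free leavers imputed at the completers' risk: (1 − a)p + a[e + (1 − e)p] = 0.16 + 0.2 × (0.0594 + 0.9406 × 0.20) = 0.210. If leavers with events also inform the imputation, it is 0.1719 / (0.8 + 0.2 × 0.0594) = 0.212.
3. All leavers set to missing, including those with an event, and imputed within arm under missing at random: 0.200.

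The same formulas at other risks:

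| True risk | Rule 1 | Rule 2 (completers' risk) | Rule 3 |
|---|---|---|---|
| 10% | 8.6% | 10.5% | 10.0% |
| 20% | 17.2% | 21.0% | 20.0% |
| 30% | 25.9% | 31.3% | 30.0% |

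**Between-arm difference, equal attrition of 20%.** With equal true risks the false difference is 0 under every rule. With true risks of 20% and 30%, rule 1 gives 25.9 − 17.2 = 8.7 points in place of 10. If all leavers go at week 2, or all at week 12, the figure is 8.2 or 9.2.

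**Between-arm difference, unequal attrition, no true effect.** Take 10% in DOS and 30% in ESC (20% overall), p = 0.20, rule 1:

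- DOS: 0.9 × 0.20 + 0.1 × 0.0594 = 0.186
- ESC: 0.7 × 0.20 + 0.3 × 0.0594 = 0.158
- false DOS excess: 2.8 points
- standard error: √(2 × 0.2 × 0.8 / 111) = 5.4 points, so about half a standard error

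The false excess is 1.4 points (SE 4.0) at p = 10% and 4.1 points (SE 6.2) at p = 30%. Under rule 2 at p = 0.20 the sign reverses: DOS 0.9 × 0.20 + 0.1 × 0.2475 = 0.205, ESC 0.7 × 0.20 + 0.3 × 0.2475 = 0.214, about −1 point.

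**Does a follow-up-based estimate remove this?** Under the same assumptions, interval survival over weeks 0–2, 2–6, 6–12 and 12–24 is 0.8^(2/24), 0.8^(4/24), 0.8^(6/24) and 0.8^(12/24). Censoring at last contact leaves these unchanged whatever the attrition. Their product is 0.8, so the estimate is 20%, and the events seen in leavers are kept.

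**The case against.** **The plan already has a valid route.** Missing binary outcomes are to be imputed, and treating every incomplete 24-week record as missing recovers the right incidence under missing at random. This stands. A reader might infer that early leavers cannot be put on the same footing as completers under this plan. The documents do not support that, because rule 3 does so. The weakness is that the plan does not choose rule 3, and that rule 3 discards hypoglycaemia events already reported by leavers, which is hard to defend for a safety endpoint.

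**The window can be inferred.** The trial lasts 24 weeks and hypoglycaemia is reviewed through week 24, so a reader will probably assume discharge to week 24. That also stands. The window is unstated, but not unknowable.

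**The imputation model is not clearly the one for this endpoint.** H.2.d does not name hypoglycaemia, and H.1.a names no predictors. It cannot be said that the plan decides to ignore observed weeks here, only that nothing written uses them.

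**The 20% is attrition from the HbA1c calculation.** A patient may miss that blood test and still report events. D.2.f and D.2.g plan repeated contact attempts, calls at 12 and 24 weeks, record monitoring and primary-care queries. This could reduce the loss. However, the chart search in D.2.g is for HbA1c and healthcare utilisation, and self-measured low readings may not reach a chart.

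**A biased comparison needs unequal dropout.** Correct. A reader might infer that the trial will show a spurious DOS excess. The documents give no attrition by arm, and both arms have the same contact times and retention procedures. Imbalance is plausible because only DOS has nurse support, and H.2 itself plans to look for differential attrition, but its size is not given.

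**Conclusion.** The endpoint lacks a stated window and a rule for partly followed patients, and nothing in the missing-data plan uses the follow-up that was observed. At an assumed true risk of 20%, the reported figure ranges from about 17% to about 21% according to a choice the plan does not make. Under as-observed scoring, equal dropout shrinks a true 10-point difference to roughly 8 to 9 points. A false difference requires unequal dropout and reaches about 2.8 points at an assumed 10% versus 30%, well within sampling error.

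These sizes rest on the constant hazard, the assumed leaving times and the assumption that the whole 20% is lost to hypoglycaemia reporting. A hazard concentrated soon after discharge would make the understatement from as-observed scoring smaller. This is a secondary endpoint in a study powered for the primary only, and the HbA1c analysis is untouched. It is a worthwhile, cheap improvement rather than a flaw that threatens the trial.

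**What to change.** In H.2.b, define the endpoint as a first documented symptomatic event below 54 mg/dl from discharge to week 24, with all randomised patients as the denominator.

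In H.2.d, add the analysis: cumulative incidence of a first event by week 24 in each arm, by life-table or Kaplan–Meier at the 2, 6, 12 and 24 week contacts, censoring at last completed contact, with the difference and its confidence interval. Report the number with no completed contact after discharge separately, since they contribute no follow-up. Where the diary gives event counts, report beside it the rate per unit of patient-time by arm, from a count model with log follow-up time as offset.

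Multiple imputation need not be ruled out. If it is kept as a sensitivity analysis, keep observed events as events and condition the imputation for event-free leavers on the weeks they completed. A competing-event analysis for death is not needed on what the documents show.

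The cost is about one paragraph and a little more analysis. The contacts are already scheduled, but Table 9 does not show that event counts or dates are recorded, so the case report form should be checked. The method still assumes that dropout is uninformative given follow-up. It should be fixed before any comparison by arm is seen.

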**Table 4. Multivariable Predictors of Change in HbA1c**

Model 1	Estimate	SE	P value
Original Model			
Intercept	25.3	5.4	<0.0001
Age	-0.086	0.028	0.004
T2DM	-0.43	0.35	0.23
Log(HbA1c baseline)	-9.82	2.00	<0.0001
New to basal insulin	-1.17	0.32	0.0008
Final Model			
Intercept	24.7	5.3	<0.0001
Age	-0.087	0.026	0.002
Log(HbA1c baseline)	-9.61	2.00	<0.0001
New to basal insulin	-1.10	0.32	0.002
Model 2	Estimate	SE	P value
Final Model			
Intercept	22.5	5.19	0.0001
Age	-0.081	0.025	0.003
First education day of discharge	0.59	0.29	0.047
Log(HbA1c baseline)	-8.86	1.95	<.0001
New to basal insulin	1.03	0.31	0.002

Abbreviations: HbA1c, glycated hemoglobin; T2DM, type 2 diabetes mellitus

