**Table 8. Diabetes Order Set Summary**

Standard Elements		
Diabetes-specific elements	Detail	Prescriber Guidance
Diet	Choice of consistent (defaults to 45 or 60 gram/meal) or flexible carbohydrate	Selection criteria for flexible carb diet.
Follow-up and referrals	Choice of primary care or endocrinology (call for appointment for *** weeks, appointment has been made for ***) Diabetes education (general education or survival skills)	Only local patients should be referred to OSU.
Patient instructions	Call provider for hypoglycemia Call provider for hyperglycemia Bring glucose log to appointment Glucose targets Home diabetes management attachment	Identification of glucose targets
Insulin prescriptions	Each insulin is presented as a panel, linked to pen needle or syringe as appropriate Each insulin Rx defaults to 3 pen or 1 vial with 1 refill Insulins categorized by basal, prandial set meal dose with correction, or prandial flexible meal dose with correction	Number of units per pen or vial Syringe size Titration options for basal insulin Selection criteria for flexible meal dosing Correction dosing from pick list of low, standard, or high doses
Glucose Monitoring supplies	Panels categorized by frequency of monitoring Each panel contains glucometer, test strips, lancets, alcohol wipes Prescriptions default to dispense appropriate number of supplies with 1 refill	Guidance on monitoring frequency
Other DM supplies	Ketone strips Glucagon	Selection criteria provided for each

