**H.2.c Primary Aim: To determine whether a Discharge order set with nursing support (DOS) is associated with lower HbA1c at 24 weeks post-program than enhanced standard care (ESC) alone.** We will test for a difference in 24 week change in HbA1c between the DOS and ESC groups using a linear mixed model for the longitudinal HbA1c measurements. Our model will contain a random subject-specific effect and fixed effects of time (baseline vs. 24 weeks), treatment, a treatment-by-time interaction, and baseline covariates related to change, which we expect to include age, whether or not patient is new to insulin, and dose of insulin based on our preliminary data. We will adjust for changes in prandial insulin dose by including dose as a time-varying covariate in our mixed models. The inclusion of covariates is not to account for differences in these factors across treatment groups (which we don't expect due to randomization) but to increase the precision of our treatment effect estimate. A Wald test of the treatment-by-time interaction will be used to test our primary hypothesis that DOS affects 24 weeks change in Hb1Ac.

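### The sample size credits baseline covariates with half the variance of HbA1c change, but the primary model as written gains no such precision from them

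*Combined protocol and SAP*

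**What the plan says.** H.2.a bases the sample size on change in HbA1c, "adjusting for baseline covariates related to change in HbA1c: age, whether or not patient is new to insulin, and dose of insulin". Its formula multiplies the variance of change by (1 − R²), where R² is "the proportion of variability in change in HbA1c explained by the baseline covariates", set at 0.5. With σ = 2.2, ρ = 0.25, Δ = 0.8, two-sided α = 0.05 and 80% power, it states 89 per group with 24-week follow-up, and 111 recruited at 20% attrition.

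H.2.c specifies a linear mixed model with a "random subject-specific effect and fixed effects of time (baseline vs. 24 weeks), treatment, a treatment-by-time interaction, and baseline covariates related to change". The expected covariates are the same three. Their stated role is "to increase the precision of our treatment effect estimate". The test is fixed: "A Wald test of the treatment-by-time interaction will be used to test our primary hypothesis". One further term is added: "We will adjust for changes in prandial insulin dose by including dose as a time-varying covariate in our mixed models".

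Baseline HbA1c is not among the expected covariates in either section. In H.2.c it appears only as a response, with the arm means at baseline left free to differ.

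**The concern.** R² in H.2.a is a share of the variance of *change*. A baseline covariate explains change in a longitudinal model only if its effect may differ between time points, that is, through a covariate-by-time term. H.2.c names one interaction, treatment-by-time, and lists the covariates without any. An analyst who follows the text would fit main effects, which explain level and not change.

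The study is powered for the primary endpoint only, so the stated 80% is the one power claim the design must support. If the variance reduction is not obtained, the primary test has roughly even odds of detecting the planned difference. The matter is one of precision and power; the change endpoint itself is not in error.

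**Working it through.** **Reproducing the plan.** n per group = 4σ²(1−ρ)(1−R²)(1.960 + 0.842)²/Δ² = 4(4.84)(0.75)(0.5)(2.802)²/0.64 = 89.04. Recruitment is 89/0.8 = 111.25. Both stated figures reproduce.

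**Why the main effect drops out.** For patient i with covariate x, arm T and visits 0 and 1, H.2.c read literally gives

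- Y₀ = μ + aᵢ + βT + γx + e₀
- Y₁ = μ + τ + aᵢ + (β + θ)T + γx + e₁

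so Y₁ − Y₀ = τ + θT + (e₁ − e₀). The term γx cancels and the variance of change is unreduced. Adding δ·x·time leaves δx in the difference, and only then does x absorb variance of change.

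**Size, at the protocol's inputs.** SE = √(2v/89), where v is the per-patient variance.

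| Model | v | SE | Power at 89 | Evaluable n for 80% | Recruited (÷0.8) |
|---|---|---|---|---|---|
| Literal wording (R² = 0) | 2(0.75)(4.84) = 7.26 | 0.404 | 51% | 179 | 224 |
| Covariate-by-time, R² = 0.5 true | 3.63 | 0.286 | 80% | 89 | 111 (as stated) |
| Baseline HbA1c adjustment only | (1 − 0.25²)(4.84) = 4.5375 | 0.319 | 71% | 112 | 140 |

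Baseline adjustment alone cuts the variance by 7.26/4.5375 = 1.60. To reach 3.63 from there, the other covariates must explain 1 − 3.63/4.5375 = 20% of what remains.

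**Counting baselines of dropouts.** With 111 baselines and 89 completers per arm and known covariance, the variance of the contrast is 2[4.5375/89 + 0.75²(4.84)/111] = 0.1510 (power 54%). With baseline means constrained equal across arms it is 2(4.5375/89) = 0.1020 (power 71%).

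**Check by fitting.** Random-intercept REML fits to 40 simulated data sets, with one covariate explaining 50% of change and 89 complete pairs per arm, gave a mean interaction SE of 0.402 without the covariate, 0.402 with its main effect (identical estimates) and 0.286 with covariate-by-time. With 111 baselines and 89 completers per arm the figures were 0.387, 0.386 and 0.279.

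**Baseline HbA1c in the pilot.** In the protocol's Table 4 (multivariable predictors), log baseline HbA1c has |t| = 9.82/2.00 = 4.91, 9.61/2.00 = 4.80 and 8.86/1.95 = 4.54. The next largest covariate |t| is 1.17/0.32 = 3.66. No R² is reported for any covariate set.

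**Sensitivity to assumptions.**

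- *Narrower baseline SD, follow-up SD 2.2, ρ 0.25.* An SD of 1.85 follows from the pilot type 2 interquartile range if roughly normal: (12.6 − 10.1)/1.349. Then v = 1.85² + 2.2² − 2(0.25)(1.85)(2.2) = 6.2275, SE 0.374, power 57%. An SD of 1.5 (assumed, no source) gives v = 5.44, SE 0.350, power 63%. Baseline adjustment stays at 71%, and its variance advantage falls to 1.37 or 1.20.
- *Prandial-dose term.* It varies over time, so it does not cancel. If dose change explained 10%, 20% or 30% of the variance of change (assumed shares) and were unrelated to arm, nominal power at 89 would be 55%, 60% or 66%. It would need to explain 50% to give the SE assumed in H.2.a.

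**The case against.** The strongest reply is that covariate-by-time terms were meant. H.2.c calls the covariates related to change and gives precision as their purpose, and the literal reading defeats that purpose. This is a fair reading, and it makes 51% conditional on an implementation the authors may not have wanted. It does not remove the gap, because the fixed effects are listed and these terms are not among them.

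Second, the 51% leaves out the prandial-dose term, which is part of the written model. That is so. But this term is not one of the baseline covariates H.2.a credits. It is measured after randomisation, and the order set could affect it, since Table 8 has "Insulins categorized by basal, prandial set meal dose with correction, or prandial flexible meal dose with correction". The primary team sets the regimen in both arms, so such an effect is possible and not shown. The documents give no figure for the variance it explains.

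Third, the pilot reports a change SD of 2.1 in established diabetes (n = 34), closer to the trial's requirement of at least 3 months' duration. With no covariate credit this gives v = 4.41, SE 0.315, power 72% and 109 evaluable for 80%; an R² of 1 − 3.63/4.41 = 0.18 would then suffice. That group is not restricted to type 2, however. The pilot type 2 change SD of 2.72 gives v = 7.40 and power 50%, in line with the base case. Even the favourable figure falls short of 80%.

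Fourth, the narrower-SD sensitivity is only weakly motivated, because the pilot was already restricted to HbA1c above 9.0%. This stands, and those rows should be read only as a range.

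Fifth, baseline HbA1c adjustment is not obligatory for a change endpoint, the covariate list is open, and t-statistics are not variance shares. This also stands. The omission is a gap in pre-specification and a missed gain, not an error.

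**Conclusion.** The concern holds. As worded, the primary model does not obtain from its baseline covariates the variance reduction on which 89 per group depends. Power at 89 is about 51% (54% counting all 111 baselines per arm), against 80% stated. These figures rest on the protocol's σ, ρ and Δ, on the literal reading of H.2.c, and on setting the prandial-dose term aside. Under the other variances examined, still without the prandial term, the literal model has 50% to 72% power.

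If covariate-by-time terms were intended and R² = 0.5 is real, the stated power is recovered. Baseline HbA1c adjustment alone recovers part of it (71%). The source of R² = 0.5 cannot be traced in the documents. Nothing here vouches for the full planned model being unbiased, since it conditions on a dose recorded after randomisation.

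**What to change.** - Write out the primary model in H.2.c and enter each baseline covariate with a covariate-by-visit term.
- Pre-specify baseline HbA1c adjustment. One option is a longitudinal model with baseline means constrained equal across arms. The other is a mixed model for repeated measures on post-baseline values with baseline HbA1c and its interaction with visit. Test the treatment difference at 24 weeks.
- In H.2.a, state which model and covariates gave R² = 0.5. Restate the power for the model that will be used, and say whether the prandial-dose term is in it.
- Clarify whether the 12-week HbA1c enters the primary model. H.2.c codes time as baseline versus 24 weeks, while H.1.a speaks of all available measurements. Including it can help when the 24-week value is missing.

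The cost is SAP wording and a new power calculation, since HbA1c at baseline, 12 and 24 weeks is already scheduled. The downsides are a slightly more complex model with a few more parameters, and possibly a less favourable stated power.
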